### **3. Revision History**

Statistical Analysis Plan (SAP) Version 1 was approved prior to unblinding.

## 4. Study Objectives

### 4.1. Primary Objective

Objectives	Endpoints
Primary	

 
To test the hypothesis that treatment with LY3041658 is superior to placebo in inducing Hidradenitis Suppurativa Clinical Response (HiSCR) in adult participants with moderate-to-severe hidradenitis suppurativa (HS)
 
	
 
Proportion of participants achieving HiSCR response at Week 16
 

### 4.2. Secondary Objectives

Objectives	Endpoints
Secondary	

 
To evaluate the efficacy of LY3041658 compared to placebo with respect to measures of signs and symptoms and pain in adult participants with moderate-to-severe HS
 
	
 
Mean change from baseline to Week 16 in: 
 
Total number of abscesses and inflammatory nodules (AN count)
 
Skin Pain – HS Numeric Rating Scale (NRS)
 
 
 

### 4.3. Exploratory Objectives

Exploratory

Exploratory objectives and endpoints may include the following:
 
 
To evaluate, at various time points, the efficacy of LY3041658 compared to placebo in inducing improvements in signs and symptoms and quality of life
 
To characterize the pharmacokinetics (PK) of LY3041658 and to explore relationships between LY3041658 exposure and select biomarkers and clinical efficacy endpoints
 
To assess the potential development of anti-LY3041658 antibodies and their impact on the safety profile and PK of LY3041658
 

## 5. Study Design

### 5.1. Summary of Study Design

Study I7P-MC-DSAD (DSAD) is a multicenter, randomized, double-blind, placebo-controlled, parallel-group Phase 2 study to evaluate the efficacy and safety of LY3041658 600 mg given intravenously (IV) every 2 weeks (Q2W) in adults with HS.

The study duration will be up to approximately 51 weeks over 4 study periods:

Screening: a period lasting up to 35 days before Week 0 (Visit 2, baseline)

Treatment Period 1: a 16-week, 2-group double-blind treatment period:

- At baseline (Visit 2, Week 0), eligible participants will be randomized in a 2:1 ratio to receive either LY3041658 600 mg IV Q2W or placebo IV Q2W, starting at the baseline visit.

Treatment Period 2: a 20-week, single-group open-label extension period:

- Starting at Week 16, all participants, including those previously assigned to placebo, will receive LY3041658 600 mg IV Q2W until the last dosing visit.

Post-treatment follow-up: a period lasting approximately 10 weeks.

- Participants will not receive study drug in this period.
- The last dose of the study drug is given at Visit 19 (Week 34). Thus, participants will have been withdrawn from study drug for a total of 12 weeks at the last post-treatment follow-up visit (Visit 802, Week 46).

Approximately 76 patients will be screened to achieve approximately 51 participants randomized in a 2:1 ratio to one of two treatment groups:

[figure not shown]
approximately 34 participants randomized to LY3041658, and

approximately 17 participants randomized to placebo.

Unscheduled visits are for participants needing rescue therapy or incision and drainage. The use of concomitant medications, including rescue therapy, is described in Section 6.5 in the protocol.

Participants who permanently discontinue the study drug early (Section 7.1 in the protocol) will undergo early termination procedures, including an early termination visit (ETV) and the post-treatment follow-up visits specified in the Schedule of Activities (SoA) (Section 1.3 in the protocol).

Figure DSAD.5.1 illustrates the study design. The blinding procedure is described in the protocol.

**Figure DSAD.5.1. Schema of Study I7P-MC-DSAD, a Phase 2 study to evaluate the efficacy and safety of LY3041658 in adults with moderate-to-severe hidradenitis suppurativa.**

Note: Starting at Week 16 participants who received placebo in Treatment Period 1 will receive LY3041658 600 mg IV Q2W.

Abbreviations: FD = first dose; IV = intravenous; LD = last dose; Q2W = every 2 weeks; R = randomization visit; V = visit; W = study week relative to randomization visit.

**5.2. Method of Assignment to Treatment**

Subjects who meet all criteria for enrollment will be randomized in a 2:1 ratio to double-blind treatment at Visit 2. Assignment to treatment groups will be determined by a computer-generated random sequence using an interactive web-response system (IWRS).

## 6. A Priori Statistical Methods

### 6.1. Statistical Hypotheses

The study will compare LY3041658 with placebo in adults with HS. The primary study objective is to demonstrate superior efficacy of LY3041658 over placebo.

The primary comparison of interest is the proportion of participants achieving HiSCR response at Week 16.

Secondary comparisons include the mean change of AN count and Skin Pain – HS NRS from baseline to Week 16.

[figure not shown]
Efficacy comparisons will be made without regard to changes to any background therapies. No adjustments for multiplicity will be made across the efficacy assessments. Participants who discontinue the treatment or the study prior to Week 16 will be considered a nonresponder for all relevant analyses.

#### 6.1.1. Estimands

The study will compare LY3041658 with placebo in participants with HS.

The primary comparison of interest is the difference in proportion of participants who achieve HiSCR response at Week 16. The primary objective is to demonstrate superiority of LY3041658 versus placebo.

The primary comparison will be assessed using a composite estimand where the intercurrent events of premature discontinuation and use of prohibited medication are part of the response definition.

### 6.2. Sample Size Determination

Approximately 76 patients will be screened to achieve approximately 51 participants randomized in a 2:1 ratio to one of two treatment groups:

approximately 34 participants randomized to LY3041658, and

approximately 17 participants randomized to placebo.

For all randomized patients, approximately 45 patients are expected to complete the 16 weeks treatment period to ensure the validity of the study result. This sample size provides at least 80% power to the primary endpoint of HiSCR response. This calculation is a 2-sided test for superiority of LY3041658 compared to placebo on HiSCR response rate with significance level

of 0.05 CCI

### 6.3. General Considerations

Efficacy analyses will be conducted on the Modified Intent-to-Treat (mITT) and Per-Protocol Set Population. The mITT set includes all data from all randomized participants receiving at least 1 dose of the IP according to the treatment the participants were assigned. The PPS set includes all data from all randomized participants who missed no more than 1 dose of study treatment to which they were assigned up to and including Week 14.

Safety analyses will be conducted on the Safety Population. This set includes all data from all randomized participants receiving at least 1 dose of the IP according to the treatment the participants actually received.

All tests of treatment effects will be conducted at a 2-sided alpha level of 0.05, unless otherwise stated. All confidence intervals (CIs) will be given at a 2-sided 95% level. Descriptive summaries of continuous data will present the group mean, standard deviation, median, minimum, maximum, and sample size. Descriptive summaries of discrete data will report the number of participants and incidence as a frequency and as a percentage. All p-values will be rounded up to 3 decimal places.

#### 6.3.1. Analysis Populations

The following populations are defined for this study:

Population	Description
Entered	All participants who sign the informed consent form
Modified Intent-to-Treat (mITT)	All participants randomly assigned to study intervention and who receive at least 1 dose of study intervention. Participants will be analyzed according to the intervention to which they were assigned.
Per Protocol Set (PPS)	All participants randomly assigned to study intervention to which they were assigned at Week 0 and who missed no more than 1 dose of study treatment up to and including Week 14.
Safety	All participants randomly assigned to study intervention and who receive at least 1 dose of study intervention. Participants will be analyzed according to the intervention they actually received within each study period.
Pharmacokinetic (PK) Analysis	All participants randomly assigned to study intervention and who receive at least 1 dose of study intervention and have PK data available.

#### 6.3.2. Definition of Baseline Measures

The baseline value for Treatment Period 1 is defined as the last nonmissing measurement on or before the date of first study drug administration (expected at Week 0). The baseline value for Treatment Period 2 is the last available value before Visit 10 (Week 16), the visit at which participants who previously received placebo will receive their first dose of LY3041658. Other definitions of the baseline value may be used to conduct additional supporting analyses.

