7.3. Lost to Follow-up

A participant will be considered lost to follow-up if he or she repeatedly fails to return for scheduled visits and is unable to be contacted by the study site. Site personnel are expected to make diligent attempts to contact participants who fail to return for a scheduled visit or were otherwise unable to be followed up by the site.

8. Study Assessments and Procedures

Study procedures and their timing are summarized in the SoA (Section 1.3). Protocol waivers or exemptions are not allowed. Adherence to the study design requirements, including those specified in the SoA, is essential and required for study conduct.

All assessments and sample collections should be finished before a dose is administered at the dosing visits.

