8.2.1. Vital Signs

Vitals signs (body temperature, blood pressure, and pulse rate) will be measured at the visits specified in the SoA (Section 1.3) and as clinically indicated. Additional vital signs may be measured during the study visits if warranted, as determined by the investigator.

Blood pressure and pulse rate should be measured after the participant has been sitting for at least 5 minutes. Orthostatic vital signs should be assessed, if possible, during any adverse event of dizziness or posture-induced symptoms. If orthostatic measurements are required, participants should be supine for at least 5 minutes and stand for at least 3 minutes. If the participant feels unable to stand, only supine vital signs will be recorded.

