9.4.1. General Considerations

Efficacy analyses will be conducted on the Modified Intent-to-Treat (mITT) Population. This set includes all data from all randomized participants receiving at least 1 dose of the IP according to the treatment the participants were assigned.

Safety analyses will be conducted on the Safety Population. This set includes all data from all randomized participants receiving at least 1 dose of the IP according to the treatment the participants actually received.

All tests of treatment effects will be conducted at a 2-sided alpha level of 0.05, unless otherwise stated. All confidence intervals (CIs) will be given at a 2-sided 95% level. Descriptive summaries of continuous data will present the group mean, standard deviation, median, minimum, maximum, and sample size. Descriptive summaries of discrete data will report the number of participants and incidence as a frequency and as a percentage.

The baseline value for Treatment Period 1 is defined as the last nonmissing measurement on or before the date of first study drug administration (expected at Week 0). The baseline value for Treatment Period 2 is the last available value before Visit 10 (Week 16), the visit at which

participants who previously received placebo will receive their first dose of LY3041658. Other definitions of the baseline value may be used to conduct additional supporting analyses.

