10.2.2. Laboratory Tests to be Obtained at Time of a Systemic Hypersensitivity Event

Selected tests should be obtained at the time of a systemic hypersensitivity event, particularly in the presence of generalized urticaria or if anaphylaxis is suspected.

After the participant has been stabilized, obtain a sample within 1 to 2 hours of the event. Samples may be obtained as late as 12 hours after the event.

Record the time at which the sample was collected.

Hypersensitiv	ity '	Tests	a
---------------	-------	-------	---

Anti-3041658 antibodies (immunogenicity) LY3041658 concentration (pharmacokinetics)	Tryptase * N-methylhistamine
Total immunoglobulins (IgA, IgE, IgG, IgM)	Complements Cytokine Panel

^a Assayed by Lilly-designated laboratory.

^{*} If a tryptase sample is obtained more than 2 hours after the event (that is, within 2 to 12 hours) or is not obtained because more than 12 hours have lapsed since the event, obtain urine for N-methylhistamine (NMH) testing. Note that for tryptase serum samples obtained within 2 to 12 hours of the event, urine NMH testing is performed in addition to tryptase testing. Collect the first void urine following the event. Obtain a follow-up urine for NMH testing at the next regularly scheduled visit or after 4 weeks, whichever is later.

10.3. Appendix 3: Adverse Events: Definitions and Procedures for Recording, Evaluating, Follow-up, and Reporting

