### **6.9. Safety Analyses**

The general methods used to summarize safety data, including the definitions of baseline values, are described in Section 6.3.2.

Safety analyses will include data after rescue unless otherwise stated, and patients will be analyzed according to the investigational product to which they were randomized at Week 0 (Visit 2). Additional analyses may be conducted using data after rescue to systemic therapy for some safety topics such as systemic treatment-emergent adverse events (TEAEs), and serious adverse events (SAEs). Safety analyses will take place using the safety population defined in Section 6.3.1.

Safety topics that will be addressed include the following: AEs, clinical laboratory evaluations, vital signs and physical characteristics.

Unless otherwise specified, by-visit summaries will include planned on-treatment visits. For tables that summarize events (such as AEs, categorical lab abnormalities, shift to maximum value), post-last dose follow-up data will be provided for Treatment Period 1 (Week 0 to Week 16) and Treatment Period 2 (Week 16 to Week 36) separately. For deaths and malignancies, all

available follow-up data up to the end of the study will be included. Listings will include all safety data.

For selected safety assessments, descriptive statistics may be presented for the last measure observed during post-treatment follow-up (up to 30 days after the last dose of treatment including rescue, regardless of the study period).

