### **6.9.2. Adverse Events**

Adverse events are recorded in the eCRFs. Each AE will be coded to system organ class (SOC) and preferred term (PT) using the Medical Dictionary for Regulatory Activities (MedDRA) version that is current at the time of database lock. Severity of AEs is recorded as mild, moderate, or severe.

A TEAE is defined as an event that either first occurred or worsened in severity after the first dose of study treatment and on or prior to the last visit date during the analysis period. For each event classification term, the number of participants experiencing a TEAE with that classification term will be tabulated. TEAEs will be summarized by treatment period and overall for the study.

Treatment-related TEAEs are defined as events that are indicated by the investigator on the eCRF to be related to treatment. For events that are gender-specific, the denominator and computation of the percentage will include only participants from the given gender.

Adverse events are classified based upon the MedDRA PT. The MedDRA Lowest Level Term (LLT) will be used in defining which events are treatment-emergent. The maximum severity for each LLT during the baseline period up to the first dose of the study medication will be used as the baseline. If an event with missing severity is preexisting during the baseline period, and persists during the treatment period, then the baseline severity will be considered mild for determining TEAE (that is, the event is treatment-emergent if the severity is coded moderate or severe postbaseline and not treatment-emergent if the severity is coded mild postbaseline). If an event occurring postbaseline has a missing severity rating, then the event is considered treatment-emergent. The day and time for events where onset is on the day of the first dose of study treatment will both be used to distinguish between pretreatment and posttreatment in order to derive treatment-emergence. Should there be insufficient data for AE start date to make this

comparison (for example, the AE start year is the same as the treatment start year, but the AE start month and day are missing), the AE will be considered treatment-emergent.

In an overview table, the number and percentage of subjects who experienced a TEAE or serious adverse event (SAE), died due to an AE, or discontinued from the study due to an AE will be summarized by treatment.

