#### 6.9.4. Vital Signs and Other Physical Findings

Vital signs and physical characteristics include systolic blood pressure (SBP), diastolic blood pressure (DBP), pulse, weight, and BMI. Original-scale data will be analyzed. When these parameters are analyzed as continuous numerical variables, unplanned measurements will be excluded. When these parameters are analyzed as categorical outcomes and/or treatment-emergent abnormalities, planned and unplanned measurements will be included.

The planned analyses described for the laboratory analytes in Section 6.9.3 will be used to analyze the vital signs and physical characteristics, except for the inclusion of a threshold for change in addition to a limit for the definition of treatment-emergent. defines the low and high baseline values as well as the criteria used to define treatment-emergence based on post-baseline values.

**Table DSAD.6.1. Categorical Criteria for Abnormal Treatment-Emergent Blood Pressure and Pulse Measurement, and Categorical Criteria for Weight Changes for Adults**

Parameter	Low mmHg	High mmHg
Systolic BP (mm Hg) (Supine or sitting – forearm at heart level)	$\leq 90$ and decrease from baseline $\geq 20$	$\geq 140$ and increase from baseline $\geq 20$
Diastolic BP (mm Hg) (Supine or sitting – forearm at heart level)	$\leq 50$ and decrease from baseline $\geq 10$	$\geq 90$ and increase from baseline $\geq 10$

Pulse (bpm) (Supine or sitting)	<50 and decrease from baseline $\geq 15$	>100 and increase from baseline $\geq 15$
Weight (kg) (Consistent clothing and timing in relationship to meals and voiding)	(Loss) decrease $\geq 7\%$	(Gain) increase $\geq 7\%$

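### The Period 1 baseline is cut off by date, not time of dosing, so an unplanned reading in a first-infusion reaction can become the baseline for the categorical vital-sign flags

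*SAP*

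**What the plan says.** SAP 6.3.2 sets the baseline for the double-blind period: "The baseline value for Treatment Period 1 is defined as the last nonmissing measurement on or before the date of first study drug administration". Protocol 9.4.1 has the same rule ("last nonmissing measurement on or before the date of first study drug administration"). Neither mentions the time of dosing. SAP 6.9 carries the rule into safety: "The general methods used to summarize safety data, including the definitions of baseline values, are described in Section 6.3.2".

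Other provisions bear on how the rule works on Day 1:

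- **Scheduled assessments are pre-dose.** The opening of protocol Section 8 says: "All assessments and sample collections should be finished before a dose is administered at the dosing visits".
- **Post-dose readings on the same day are foreseen.** Protocol 6.1 requires at least 30 minutes of observation after each infusion. Protocol 8.2.1 allows extra vital signs at the investigator's discretion and adds: "Orthostatic vital signs should be assessed, if possible, during any adverse event of dizziness or posture-induced symptoms".
- **Tables differ in which readings they admit.** SAP 6.9.4 drops unplanned vital signs from the continuous analysis. For categorical outcomes and treatment-emergent abnormalities it says "planned and unplanned measurements will be included". SAP 6.9.3 restricts the general laboratory tables to scheduled time points and sends unscheduled values to listings.
- **Adverse events use a finer rule.** SAP 6.9.2 says: "The day and time for events where onset is on the day of the first dose of study treatment will both be used". Protocol 9.4.5 likewise refers to time of onset before the first dose.

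**The concern.** A baseline for a safety flag should be free of the treatment. The date rule does not guarantee this on Day 1, because a value recorded after the infusion has the same date as the dose and is later than the pre-dose value.

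The readings at risk are the unplanned ones, and they tend to be taken because the participant is unwell. Infusion reactions and systemic hypersensitivity reactions are adverse events of special interest (protocol 8.3.6), and the first exposure is a natural time to look for them. An error here would therefore fall on participants who reacted. It could remove a true low-pressure or high-pulse flag and shift the reference for that participant's later flags.

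The SAP would also be inconsistent with itself. The same episode of hypotension could count as a treatment-emergent adverse event under 6.9.2 and supply the baseline blood pressure under 6.3.2.

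**Working it through.** The plan gives no figure to reproduce here. The check traces the rule through Table DSAD.6.1.

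**Criteria (SAP Table DSAD.6.1)**

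- Systolic low: at most 90 and a fall of at least 20. Systolic high: at least 140 and a rise of at least 20.
- Diastolic low: at most 50 and a fall of at least 10. Diastolic high: at least 90 and a rise of at least 10.
- Pulse high: above 100 and a rise of at least 15.

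**Assumed participant (illustrative values, not from the documents)**

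- Pre-dose: 125/82, pulse 75.
- During a reaction to the first infusion, last reading that day: 88/48, pulse 120.
- Week 2: 142/90, pulse 72.

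**Reaction reading**

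| Measure | Change from pre-dose | Flag with pre-dose baseline | Change under date rule | Flag under date rule |
|---|---|---|---|---|
| Systolic 88 | 125 − 88 = 37 fall | Low | 88 − 88 = 0 | None |
| Diastolic 48 | 82 − 48 = 34 fall | Low | 48 − 48 = 0 | None |
| Pulse 120 | 120 − 75 = 45 rise | High | 120 − 120 = 0 | None |

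**Week 2 reading**

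| Measure | Change from pre-dose | Flag with pre-dose baseline | Change under date rule | Flag under date rule |
|---|---|---|---|---|
| Systolic 142 | 142 − 125 = 17 rise | None | 142 − 88 = 54 rise | High |
| Diastolic 90 | 90 − 82 = 8 rise | None | 90 − 48 = 42 rise | High |

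The date rule loses three true flags and creates two false ones. The false high flags need a value that already meets the absolute limit; a systolic value below 140 is not flagged high from any baseline. A repeat systolic reading of 88 at a later infusion would also be missed (0 instead of a fall of 37).

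**If the participant recovers and is measured again that day** (assume 124/82, pulse 78), the recovered value is the baseline. Week 2 is then not flagged: 142 − 124 = 18 and 90 − 82 = 8. The reaction reading is still missed if everything up to the end of the first-dose date is treated as baseline. The SAP does not say where post-baseline starts for vital signs.

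**Which outputs the rule can reach**

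| Output | Unplanned readings used? | Exposed? |
|---|---|---|
| Continuous vital signs (SAP 6.9.4) | No | No |
| General laboratory tables (SAP 6.9.3) | No | No |
| Categorical vital signs (SAP 6.9.4) | Yes | Yes |
| Creatinine grades (SAP 6.9.5.2) | Yes | Possibly: baseline is the highest grade in a baseline period whose end is not stated |
| Adverse events (SAP 6.9.2) | Not applicable | No: split by day and time |
| Efficacy | Scheduled assessments, pre-dose | No |

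**The case against.** The strongest reply is that little is lost. Reactions are analysed mainly as adverse events. Those starting on Day 1 are separated by time, infusion site reactions are tabulated by symptom and visit (SAP 6.9.5.5), hypersensitivity events are found by standard queries and listed (6.9.5.4), and all safety data go into listings (6.9). This stands. A reader might infer that a first-infusion abnormality vanishes from the tables altogether; the documents do not support that.

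Nor do they support the inference that every later change from baseline is distorted for such a participant. Continuous vital signs and the general laboratory tables exclude unplanned readings, and the scheduled Visit 2 value is pre-dose.

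A third tempting reading concerns treatment-emergent anti-drug antibodies. The hypersensitivity panel includes an antibody sample, and protocol 10.2.2 says "After the participant has been stabilized, obtain a sample within 1 to 2 hours of the event". A Day 1 event sample could literally replace the pre-dose sample. But nothing in the documents shows that a titer drawn within hours of first exposure would differ from the pre-dose titer, so no bias is shown.

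It is also fair to say that the reaction reading becomes the baseline only if it is the last of the day, and that orthostatic sets include standing readings while Table DSAD.6.1 specifies supine or sitting. The first limits how often the problem arises. The second weakens one source of readings, but protocol 8.2.1 separately allows any additional vital signs. The sentence in SAP 6.3.2 allowing other baseline definitions covers supporting analyses only and does not repair the main table.

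**Conclusion.** The rule is wrong as written, within a narrow scope. Followed literally, it can suppress a true treatment-emergent vital-sign flag at the first infusion and produce false high flags afterwards. The clear route is the categorical analysis in SAP 6.9.4; creatinine grading is a weaker one that depends on an undefined term.

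The conclusion rests on two assumptions: that an unplanned reading is taken after the infusion on Day 1 and is the last of that day, and that the inclusion of unplanned readings in SAP 6.9.4 extends to the choice of baseline, which its wording does not exclude.

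The documents do not allow a frequency to be derived. Protocol 2.3 mentions one mild, short-lived infusion-associated reaction in the single-dose Phase 1 study, which suggests few cases but gives no rate for this trial. Each misclassified participant on drug would move the group percentage by 1/42 = 2.4 points at the protocol's planned size, or 1/34 = 2.9 points at the SAP's. Efficacy conclusions and adverse event counts do not depend on this rule.

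**What to change.** In SAP 6.3.2, define the Period 1 baseline as the latest available value taken before the date and time at which the first infusion starts. Where a Day 1 value has no clock time, treat scheduled Visit 2 assessments as pre-dose and unplanned same-day readings as post-baseline. Use the same cut-off to define the baseline period in SAP 6.9.3 and 6.9.5.2. This brings all three sections into line with the day-and-time rule in SAP 6.9.2.

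Protocol 9.4.1 should be aligned. If an amendment is not wanted for this alone, protocol 9.4 allows a change that does not alter a principal feature to be described and justified in the SAP and clinical study report.

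The cost is a few sentences and a date-time comparison in the programs. Protocol 6.4 already requires the date and time of every dose to be recorded. Protocol 8.2.1 does not say that vital signs carry a clock time, which is why the fallback is needed.
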